6.1.2.2. AEs Within 1 Month of Age

- Analysis set: Safety (Section 4).
- Analysis methodology: Descriptive summary statistics for Tier 3 events; difference and 95% CI between the vaccine group and the placebo group for Tier 2 events.
- Intercurrent events and missing data: For participants who discontinue, all collected data will be included; missing AE dates will be imputed as described in Pfizer's Vaccine Statistics Rulebook.
- For each group, number of participants with AEs **CCI** within 1 month (30 days) (n), %, and 95% CI will be presented for any AE, each SOC, and each PT within each SOC, by vaccine group. For AEs classified as Tier 2 events, difference in proportions and associated 2-sided 95% CI between the vaccine group and the placebo group will be presented.

6.1.2.3. AEs of Special Interest (Major Congenital Anomalies, Developmental Delays), MAEs, and SAEs Through 12 Months of Age

- Analysis set: Safety (Section 4).
- Analysis methodology: Descriptive summary statistics.
- Intercurrent events and missing data: For participants who discontinue, all collected data will be included; missing AE dates will be imputed as described in Pfizer's Vaccine Statistics Rulebook.
- For each group, number of participants with AEs of special interest, MAEs, and SAEs through 12 months of age (n), %, and 95% CI will be presented for any event, each SOC, and each PT within each SOC, by vaccine group. For AEs of special interest, difference in proportions and associated 2-sided 95% CI between the vaccine group and the placebo group will be presented.

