2.1.4. Primary Estimands

2.1.4.1. Primary Estimands: Maternal Participants

- **Percentage of maternal participants reporting local reactions.**

This estimand includes the following 4 attributes:

- Population: Maternal participants who receive 1 dose of investigational product.
- Variable: Presence/absence of prespecified local reactions within 7 days after vaccination.
- Intercurrent event(s): For participants who discontinue, all collected data will be included; missing data will not be imputed.
- Population-level summary: Percentage of maternal participants reporting local reactions in each vaccine group.

- **Percentage of maternal participants reporting systemic events.**

This estimand includes the following 4 attributes:

- Population: Maternal participants who receive 1 dose of investigational product.
- Variable: Presence/absence of prespecified systemic events within 7 days after vaccination.
- Intercurrent event(s): For participants who discontinue, all collected data will be included; missing data will not be imputed.
- Population-level summary: Percentage of maternal participants reporting systemic events in each vaccine group.

- **Percentage of maternal participants reporting adverse events (AEs) from the time of vaccination through 1 month after vaccination.**

This estimand includes the following 4 attributes:

- Population: Maternal participants who receive 1 dose of investigational product.
- Variable: Presence of AEs within 1 month after vaccination.
- Intercurrent event(s): For participants who discontinue, all collected data will be included; missing AE dates will be imputed as described in Pfizer's Vaccine Statistics Rulebook.
- Population-level summary: Percentage of maternal participants reporting AEs through 1 month after vaccination in each vaccine group.

- **The percentage of maternal participants reporting obstetric complications, medically attended adverse events (MAEs), and serious adverse events (SAEs) throughout the study.**

This estimand includes the following 4 attributes:

- Population: Maternal participants who receive 1 dose of investigational product.
- Variable: Presence/absence of the event of interest throughout the study.
- Intercurrent event(s): For participants who discontinue, all collected data will be included; missing AE dates will be imputed as described in Pfizer's Vaccine Statistics Rulebook.

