2.1.4.2. Primary Estimands: Infant Participants

- **Percentage of infant participants with specific birth outcomes.**

This estimand includes the following 4 attributes:

- Population: Infant participants born to the maternal participants receiving 1 dose of investigational product.
- Variable: Presence/absence of specific birth outcomes.
- Intercurrent event(s): No intercurrent events to be taken into account.
- Population-level summary: Percentage of infant participants with specific birth outcomes in each vaccine group.

- **Percentage of infant participants having AEs.**

This estimand includes the following 4 attributes:

- Population: Infant participants born to the maternal participants receiving 1 dose of investigational product.
- Variable: Presence/absence of AEs from birth to 1 month, CCI [REDACTED]
- Intercurrent event(s): For participants who discontinue, all collected data will be included; missing AE dates will be imputed as described in Pfizer's Vaccine Statistics Rulebook.
- Population-level summary: Percentage of infant participants with AEs CCI [REDACTED] from birth to 1 month in each vaccine group.

- **Percentage of infant participants having SAEs, AEs of special interest, and MAEs through 12 months of age.**

This estimand includes the following 4 attributes:

- Population: Infant participants born to the maternal participants receiving 1 dose of investigational product.
- Variable: Presence/absence of SAEs, AEs of special interest, and MAEs. These will be collected through 12 months of age, except for those congenital anomalies that occur during intrauterine life and can be identified prenatally, at birth, or later in life.
- Intercurrent event(s): For participants who discontinue, all collected data will be included; missing AE dates will be imputed as described in Pfizer's Vaccine Statistics Rulebook.
- Population-level summary: Percentage of infant participants with the event of interest during the first 12 months of life in each vaccine group.

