4. ANALYSIS SETS (POPULATIONS FOR ANALYSIS)

Data for all participants will be assessed to determine if participants meet the criteria for inclusion in each analysis population prior to unblinding and releasing the database and classifications will be documented per standard operating procedures.

Population	Description
Enrolled	All participants who sign the informed consent document.
Randomly assigned to investigational product	All maternal participants who are assigned a randomization number in the interactive response technology (IRT) system.
Evaluable – Maternal	All maternal participants who: 
 • are eligible; • receive the investigational product to which they were randomized; • have blood drawn for assay testing within the protocol-specified time frames ; • have at least 1 valid and determinate assay result after vaccination; and • have no major protocol violations. Participants will be analyzed according to the investigational product as randomized.
Evaluable – Infant	All infant participants who: 
 • are eligible; • are born to the maternal participants who received the investigational product to which they were randomized and who have no major protocol violations before delivery; • have blood drawn for assay testing within the protocol-specified time frame at birth^a; • have at least 1 valid and determinate assay result at birth^a; and • have no major protocol violations. Participants will be analyzed according to the investigational product as randomized to their mothers.
Modified intent-to-treat (mITT) – Maternal	All randomized maternal participants who receive investigational product and have at least 1 valid and determinate assay result for the proposed analysis. Participants will be analyzed according to the investigational product as randomized.
mITT – Infant	All infant participants who are born to vaccinated maternal participants and have at least 1 valid and determinate assay result for the proposed analysis. Participants will be analyzed according to the investigational product as randomized to their mothers.
Safety – Maternal	All randomized maternal participants who receive investigational product. Participants will be analyzed according to the investigational product they actually received. A randomized participant who did not receive investigational product will be excluded from the safety analyses.

Population	Description

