Safety – Infant	All infant participants who are born to vaccinated maternal participants. Participants will be analyzed according to the investigational product their mothers actually received. An infant born from a randomized maternal participant who did not receive investigational product will be excluded from the safety analyses.

- a. Cord blood sample must be obtained on the day of birth. If cord blood is unavailable, a venous blood sample is to be collected up to 24 hours after birth.

Major protocol violations will be determined by clinical review (through the data handling memo). A major protocol violation is a protocol violation that, in the opinion of the sponsor’s study medical monitor, would materially affect assessment of immunogenicity, eg, participant receipt of a prohibited vaccine or medication that might affect immune response or a medication error with suspected decrease in potency of the vaccine. The sponsor’s medical monitor will identify those participants with protocol violations before any immunogenicity analysis is carried out.

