5.2. General Methods

Descriptive summary statistics will be provided for all endpoints. Unless otherwise explicitly stated, descriptive statistics for continuous variables are n, mean, median, standard deviation, minimum, and maximum. Descriptive statistics for categorical variables are the proportion (%) and the n (the numerator) and N (the denominator) used in the calculation of the proportion.

All analyses for both immunogenicity and safety data will be descriptive in nature.

All of the safety, tolerability, and immunogenicity data will be summarized by vaccine group of the maternal participants. Immunogenicity results will be analyzed separately for all the formulations. Within each participant group (maternal or infant), all participants who receive placebo will be combined as the control group. All data will be presented separately for maternal and infant participants. The only exception is the combined analysis of maternal-to-infant placental transfer ratio (infant/mother) of RSV A– and RSV B-neutralizing antibody titers.

Within maternal and infant groups, immunogenicity results may be summarized by formulation, dose level, and gestational age (GA).

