6.1.1.4. Obstetric Complications, MAEs, and SAEs Throughout the Study

- Analysis set: Safety ([Section 4](#)).
- Analysis methodology: Descriptive summary statistics.
- Intercurrent events and missing data: For participants who discontinue, all collected data will be included; missing AE dates will be imputed as described in Pfizer's Vaccine Statistics Rulebook.
- For each group, number of participants with obstetric complications, MAEs, and SAEs throughout the study (n), %, and 95% CI will be presented for any event, each SOC, and each PT within each SOC, by vaccine group.

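### Infant MAEs, SAEs and developmental delay through 12 months: the crude percentage in the safety population counts infants lost early as event-free, so it is biased low if there is loss

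*SAP*

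**What the plan says.** **Target.** For infant SAEs, AEs of special interest and MAEs, SAP 2.1.4.2 sets the population-level summary as "Percentage of infant participants with the event of interest during the first 12 months of life in each vaccine group". This is a risk over a fixed period.

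**Estimator.** SAP 6.1.2.3 names the safety population as analysis set and plans this output: "number of participants with AEs of special interest, MAEs, and SAEs through 12 months of age (n), %, and 95% CI will be presented". The breakdown covers any event, system organ class and preferred term. For AEs of special interest it also plans a vaccine-minus-placebo difference with 95% CI.

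**Denominator.** The infant safety population in SAP 4 is "All infant participants who are born to vaccinated maternal participants", with no minimum follow-up. SAP 5.2 requires display of "the n (the numerator) and N (the denominator) used in the calculation of the proportion". It does not write out N for these endpoints, so reading N as the safety-population count is an inference from the named analysis set.

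**Loss to follow-up.** The only rule on discontinuation is "For participants who discontinue, all collected data will be included", together with imputation of missing AE dates. No passage says how to classify at 12 months an infant last seen at, say, week 6. Two other parts of the SAP do have a rule: reactogenicity has an explicit missing category (SAP 3.5.2.1), and antibody results after discontinuation are censored (SAP 2.1.5).

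**The concern.** A crude n/N equals the 12-month risk only if every infant is observed for 12 months, or if no event would have followed loss. Otherwise, keeping collected data and imputing nothing has the same effect as imputing no event after last contact. The error has one direction, downward, and the Clopper-Pearson interval does not reflect it because it measures sampling error only.

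The plan expects some loss. Protocol 7.2 says withdrawn participants are not replaced, Protocol 7.3 treats unreachable participants as withdrawn, and Protocol 8.3.1 ends active collection when consent is withdrawn.

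These are primary safety endpoints, and SAP 2 says the study will inform progression and the choice of dose and formulation. The planned between-group difference for AEs of special interest includes developmental delay, so unequal loss between groups would enter that contrast as an apparent vaccine effect.

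**Working it through.** **The plan's own figure.** The documents state no 12-month percentage, event rate or dropout rate. The only statistical figure for safety is Protocol Table 6, the chance of seeing at least one AE. For a 1% rate and N = 100 it is 1 − 0.99^100 = 0.634, against 0.63 stated. All 21 cells reproduce, and this point leaves the table unaffected.

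**Inputs.** From the documents: the safety population as analysis set, n/N as the percentage, and up to 650 women in five equal groups, so 650/5 = 130 per group. Taking about 130 infants per group is an approximation. Assumed for illustration: R, the true 12-month risk (10% or 30%); d, the share lost before 12 months (5%, 10% or 20%); and loss unrelated to events.

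**Formula.** Let Q be the average risk accrued before loss among infants who are lost.

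- Expected n/N = (1 − d)R + dQ.
- Understatement = d(R − Q). Since Q lies between 0 and R, the relative understatement lies between 0 and d.
- All loss at birth: Q = 0.
- Constant hazard with loss uniform over the year: L = −ln(1 − R) and Q = 1 − (1 − e^−L)/L.

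**Worked case, R = 30%, d = 10%.** L = 0.3567 and Q = 1 − 0.30/0.3567 = 0.159.

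- Uniform loss: 0.90 × 0.30 + 0.10 × 0.159 = 0.286, which is 4.7% lower in relative terms, about half of d.
- All loss at birth: 0.90 × 0.30 = 0.270, which is 10% lower, the full share lost.

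| True risk R | Share lost d | Expected n/N, uniform loss | Expected n/N, all lost at birth |
|---|---|---|---|
| 10% | 5% | 9.8% | 9.5% |
| 10% | 10% | 9.5% | 9.0% |
| 10% | 20% | 9.0% | 8.0% |
| 30% | 5% | 29.3% | 28.5% |
| 30% | 10% | 28.6% | 27.0% |
| 30% | 20% | 27.2% | 24.0% |

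**Early events.** With R = 10% and d = 10%, if half of the events precede any loss, n/N = 0.09 + 0.10 × 0.05 = 9.5%. If all do, n/N = 0.09 + 0.10 × 0.10 = 10.0%, with no bias. Anomalies found at birth are close to this second case.

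**Unequal loss.** Suppose the true risk is equal in both groups, with 15% lost on vaccine and 5% on placebo.

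- R = 30%, uniform loss: (0.85 × 0.30 + 0.15 × 0.159) − (0.95 × 0.30 + 0.05 × 0.159) = −1.4 points. All lost at birth: 25.5% − 28.5% = −3.0 points.
- R = 10% (L = 0.1054, Q = 0.051), uniform loss: 9.3% − 9.8% = −0.5 point. All lost at birth: 8.5% − 9.5% = −1.0 point.

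**Sampling error.** The exact 95% CI is 5.4% to 16.5% for 13/130 and 22.3% to 38.7% for 39/130.

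**The case against.** The strongest reply is that the study is descriptive, with no test or decision rule (SAP 5.1), and that at moderate loss the shift is small beside the interval at about 130 infants per group. Loss will also be visible: SAP 6.5.2 tabulates withdrawals with reasons by vaccine group, and the Protocol schedules contact about weekly until about 6 months after delivery. All of this stands, and it limits the weight of the point. It does not remove it. The shift is systematic, and a withdrawal count does not let a reader recover the 12-month risk without the timing of events and losses.

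One may also argue that keeping all collected data is part of the estimand, so the crude percentage is the target. But that clause says which data to use, not what status an unobserved infant has, and the summary still refers to the first 12 months of life.

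A reader might infer three stronger points that the documents do not support:

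- **That the maternal percentages have the same fault.** The maternal variable is "Presence/absence of the event of interest throughout the study", over a follow-up that varies with gestational age at vaccination. It is not a fixed-time risk, and the planned summary ("number of participants with obstetric complications, MAEs, and SAEs throughout the study (n), %, and 95% CI will be presented") matches it.
- **That unequal loss would create a false MAE or SAE difference in the planned output.** SAP 6.1.2.3 plans a between-group difference only for AEs of special interest.
- **That a time-to-event estimate should replace the crude percentage.** Protocol 9.4.2 specifies the Clopper-Pearson percentage, and Protocol 9 requires an amendment for a major change to a primary analysis.

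**Conclusion.** The point holds for infant MAEs, SAEs and developmental delay. The planned crude percentage is biased low for the 12-month estimand whenever infants are lost before 12 months and events would have followed. If loss is unrelated to events, the relative understatement is about half the share lost under uniform loss and constant hazard, and never more than the share lost. It is zero if nobody is lost or if every event precedes loss. Unequal loss would also enter the planned vaccine-minus-placebo difference for developmental delay, by at most the true risk times the difference in the share lost.

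The conclusion rests on N being the safety-population count. The numerical sizes are illustrations, because the documents give no event or loss rate. They do not show that the reported percentages will be materially wrong. No sample size, test or Table 6 entry changes.

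**What to change.** In SAP 6.1.2.3:

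1. Keep crude n (%) with the Clopper-Pearson CI as the main summary, and state that N is the infant safety population.
2. Show by vaccine group the number of infants followed to 12 months.
3. Add, by vaccine group, a supplementary cumulative incidence at 12 months of age with 95% CI for any MAE, any SAE and developmental delay, censored at last visit or withdrawal. Use Aalen-Johansen with death as a competing event for MAE and developmental delay. Use Kaplan-Meier for SAE, since death is itself an SAE.
4. Name the day of age at which the estimate is read, because the 12-month visit window runs from day 350 to day 378.

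The cost is SAP wording and one extra table built from event dates and visit or withdrawal dates. As a supplement it leaves the protocol's primary safety analysis unchanged. The downside is that the estimate assumes non-informative loss, which should be stated under the table. Partial onset dates would follow the date rules already planned.

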6.2. Secondary Endpoints

6.2.1. Secondary Endpoints: Maternal Participants

6.2.1.1. RSV A- and RSV B-Neutralizing Antibody Titers Measured Before Vaccination, at 2 Weeks and 1 Month After Vaccination, and at Delivery

6.2.1.1.1. Main Analysis

- Estimand strategy: Hypothetical.
- Analysis set: Evaluable (Section 4). Maternal participants receiving 1 dose of investigational product and in compliance with key protocol criteria.
- Analysis methodology: Descriptive summary statistics.

- Intercurrent events and missing data: All postdiscontinuation or postviolation observations will be censored. Results obtained from out-of-window blood draws will also be removed. Missing results will not be imputed.
- GMTs of the RSV A– and RSV B–neutralizing antibody titers at each available time point will be descriptively summarized for each vaccine group, along with associated 2-sided 95% CIs.
- GMFRs and associated 2-sided 95% CIs will be provided for RSV A– and RSV B–neutralizing antibody titers from before vaccination to each available time point after vaccination for each vaccine group.
- GMRs of the RSV vaccine group to the placebo group for the RSV A– and RSV B–neutralizing antibody titers at each available time point after vaccination will be calculated, along with associated 2-sided 95% CIs.
- RCDCs for RSV A– and RSV B–neutralizing antibody titers for a combination of prespecified time points and vaccine groups will be generated.
- Bar graphs of prevaccination and 1-month-postvaccination neutralizing GMTs will be produced for each vaccine group.

6.2.1.1.2. Supplementary Analysis

The main analysis will also be performed based on the mITT population if there is sufficient difference between the mITT population and the evaluable populations (an approximate 10% difference in the numbers of participants in each population).

The effects of formulation and dose on RSV A– and RSV B–neutralizing titers will be evaluated using an analysis of variance model with the log-transformed values of neutralizing titers at 1 month after vaccination. The model will include formulation and dose as main effects and their interaction. The F statistic and p-value for the main effects and interaction will be calculated. The least-square (LS) means, difference between the means, and 95% CI associated with these differences will be presented for each main effect. These will be exponentiated and presented in the original scale.

6.2.2. Secondary Endpoints: Infant Participants

6.2.2.1. RSV A– and RSV B–Neutralizing Antibody Titers Measured at Birth and at 1 Month, 2 Months, 4 Months, and 6 Months of Age Depending on the Assigned Blood Sampling Schedule

6.2.2.1.1. Main Analysis

- Estimand strategy: Hypothetical.
- Analysis set: Evaluable ([Section 4](#)). Infant participants born to maternal participants receiving 1 dose of investigational product and in compliance with the key protocol criteria.

- Analysis methodology: Descriptive summary statistics.
- Intercurrent events and missing data: All postdiscontinuation or postviolation observations will be censored. Results obtained from out-of-window blood draws will also be removed. Missing data will not be imputed.
- GMTs of the RSV A– and RSV B–neutralizing antibody titers at each available time point will be descriptively summarized for each vaccine group, along with associated 2-sided 95% CIs.
- GMRs of the RSV vaccine group to the placebo group for the RSV A– and RSV B–neutralizing antibody titers at each available time point after birth will be calculated, along with associated 2-sided 95% CIs.
- RCDCs for RSV A– and RSV B–neutralizing antibody titers for a combination of prespecified time points and vaccine groups will be generated.

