1.3.2. Schedule of Activities for Infant Participants

Visit Number	1	2	3	4	5	6
Visit Description	Birth	1-Month Follow-up	2-Month Follow-up	4-Month Follow-up	6-Month Follow-up	12-Month Follow-up
Visit Window (Days)	Birth to 7 Days After Birth	28 to 35 Days After Birth	49 to 63 Days After Birth	112 to 126 Days After Birth	168 to 210 Days After Birth	350 to 378 Days After Birth
Assign infant participant identifier	X					
Demography	X					
Collect background factors	X	X	X	X	X	X
Collect birth outcome information (including Ballard score)	X					
Vital signs ^a	X	X	X	X	X	X
Physical examination	X	X	X	X	X	X
Length, head circumference, and weight ^{b,c}	X	X	X	X	X	X
Record nonstudy vaccine information	X	X	X	X	X	X
Record monoclonal antibodies (eg, Synagis) or blood transfusions (eg, whole blood, packed cells)	X	X	X	X	X	X
Review eligibility	X					
Cord blood sample ^c (~10 mL) for serologic assessment	X					
Blood draw for serologic assessment (up to 5 mL per blood sample based on weight) ^b		X	X	X	X	
Record concomitant medication taken to treat an AE	X	X	X	X	X	X
Record adverse events, medically attended adverse events, serious adverse events, and adverse events of special interest, as appropriate ^d	X	X	X	X	X	X

Visit Number	1	2	3	4	5	6
Visit Description	Birth	1-Month Follow-up	2-Month Follow-up	4-Month Follow-up	6-Month Follow-up	12-Month Follow-up
Visit Window (Days)	Birth to 7 Days After Birth	28 to 35 Days After Birth	49 to 63 Days After Birth	112 to 126 Days After Birth	168 to 210 Days After Birth	350 to 378 Days After Birth
Surveillance reminder contact	After delivery, contact the infant participants' parents approximately every week until approximately 6 months after delivery					

- a. Vital signs include rectal temperature, heart rate, oxygen saturation by pulse oximetry (**Visit 1 only**), and respiratory rate.
- b. Infant participants will be randomly assigned to 1 of 2 blood sampling schedules. Blood samples will be collected either at Visit 2 (1-month follow-up) and Visit 4 (4-month follow-up) **OR** at Visit 3 (2-month follow-up) and Visit 5 (6-month follow-up). Weight will be used to determine the volume of blood that can be collected.

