The proposed primary mechanism for protection of infants by the RSV maternal vaccine is neutralization of the virus by transplacentally transferred antibody, which is increased by immunization. Maternal antibody decays exponentially in infants. Therefore, it is anticipated that higher titers of transferred neutralizing antibodies will provide greater levels and durations of infant protection. Based on the totality of preclinical and clinical data obtained to date, and given the absence of any sign of dose response in measures of safety or reactogenicity in the FIH study, it is proposed to test 120- μg and 240- μg antigen doses of the bivalent RSV vaccine candidate, with and without $\text{Al}(\text{OH})_3$, in pregnant women. These doses are expected to provide the greatest potential level of transplacental antibody transfer to infants and, therefore, the greatest potential benefit.

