8.2.13.2. Infant Participant: Total Volume of Blood Collected

Blood samples will be collected according to the directive 2001/20/EC: Ethical Consideration for Clinical Trials Performed in Children.²⁷

Infant participants will be randomly assigned to 1 of 2 blood sampling schedules.

All infants will have a cord blood sample collected at birth. The cord blood is collected from the umbilical cord vein attached to the placenta after the umbilical cord has been clamped and cut. If cord blood is unavailable, a venous blood sample may be collected from the infant participant up to 24 hours after birth. The infant's weight must be used to determine the volume of blood that can be collected (see [Table 5](#) below). Venous blood samples will also be collected at approximately 1 and 4 months after birth or 2 and 6 months after birth.

The total volume of venous blood collected from each infant participant for antibody assessment will vary depending on the infant's weight at each visit.

The maximum volume of venous blood to be collected will be no more than 15 mL over the course of 12 months.

Table 5. Guideline for Infant Blood Draw

Body Weight (in kg)	Approximate Volume of Blood (in mL) to Be Collected per Blood Draw
<1.3	No blood draw
1.3 to ≤2.4	1.0
>2.4 to ≤3.7	2.0
>3.7 to ≤4.9	3.0
>4.9 to ≤6.2	4.0
>6.2	5.0

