- Perform obstetric examination including but not limited to fundal height, fetal heart tones, and fetal movement.
- Ensure that all inclusion criteria and none of the exclusion criteria are met.
- Ensure that the maternal participant meets none of the temporary delay criteria as described in [Section 5.2.3](#).
- Ask the maternal participant to provide a urine sample for glucose and protein testing (urine dipstick).

- Issue the maternal participant an e-diary and provide instructions on its completion.
- Prior to vaccination, collect a blood sample of approximately 25 mL for serologic assessments.
- Obtain the maternal participant's randomization number and investigational product kit number using the IRT system. Either blinded or unblinded site staff may obtain this information. The infant blood sample schedule will be provided at this time. Refer to the IRT manual for further instructions on this process.
- Unblinded site staff member(s) will administer a single 0.5-mL dose of investigational product into the deltoid muscle of the nondominant arm. Please refer to the IP manual for further instruction on this procedure.
- Blinded site staff must observe the maternal participant for any acute reactions for at least 30 minutes after investigational product administration.
 - **Note:** The first 5 maternal participants vaccinated in the study will be observed for at least 4 hours after investigational product administration.
- Record any acute reactions in the maternal participant's source documents, on the AE page of the CRF, and on an SAE form as applicable.
- Issue a measuring device to measure local reactions and a digital thermometer for recording daily temperatures, and provide instructions on their use.
- Ask the maternal participant to complete the e-diary from Day 1 to Day 7, with Day 1 being the day of vaccination.
- Ask the maternal participant to contact the site staff or investigator immediately if she experiences any of the following from Day 1 to Day 7 after vaccination to determine if an unscheduled reactogenicity visit is required:
 - Fever $\geq 39.0^{\circ}\text{C}$ ($\geq 102.1^{\circ}\text{F}$).
 - Redness or swelling at the injection site on the nondominant arm measuring greater than 10 cm (>20 measuring device units).
 - Severe pain at the injection site on the nondominant arm.
 - Any severe systemic event.
 - Any blackening of the skin (necrosis) at the injection site.
 - Any peeling/scaling of the skin (exfoliative dermatitis).

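### The 1- to 6-month infant GMTs and GMRs use only the infants bled at each visit; they are valid, but less precise than the collected birth samples allow

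*SAP*

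**What the plan says.** - **Design.** Protocol 1.3.2, footnote b: "Infant participants will be randomly assigned to 1 of 2 blood sampling schedules". Protocol 8.2.13.2 gives the two patterns: "Venous blood samples will also be collected at approximately 1 and 4 months after birth or 2 and 6 months after birth". The same section says "All infants will have a cord blood sample collected at birth", with an early venous sample as the fallback. Neither document states the ratio between the schedules.
- **Timing of assignment.** At the mother's vaccination visit (Protocol 8.10.1.2), "The infant blood sample schedule will be provided at this time". No infant titer exists at that point.
- **Analysis set.** To be evaluable, an infant must, among other conditions, "have at least 1 valid and determinate assay result at birth" (SAP 4).
- **Estimators.** SAP 6.2.2.1.1 summarises GMTs "at each available time point will be descriptively summarized for each vaccine group" and forms GMRs against placebo in the same visit-by-visit way, adding "Missing data will not be imputed". SAP 5.2.2.1 gives the GMT a Student t interval on the log scale. SAP 5.2.2.3 gives the GMR a two-sample t interval on the difference in log means. Neither has a covariate or a longitudinal term.
- **Supplementary analyses.** The readable ones in SAP 6.2.2.1.2 are a repeat in the mITT population and a comparison of cord with venous birth samples. Neither carries birth titers forward to later visits. Redacted text follows.

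**The concern.** Protocol 4.3 states that "Maternal antibody decays exponentially in infants". If so, an infant's later titer should be related to its birth titer, and the birth titer of an infant not bled at a visit carries information about what that bleed would have shown. The unbled infants were chosen at random, so this information can be used without bias. The readable plan leaves it out.

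Persistence of transferred antibody is part of the programme's core hypothesis (Protocol 2.2), and SAP 2 says the study will supply data for choosing dose and formulation. SAP 5.1 relies on estimation rather than testing, so interval width is the natural measure of what the study delivers.

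The 1- and 4-month means also come from different infants than the 2- and 6-month means. A chance difference in birth titer between the two halves of an arm therefore feeds, in proportion to ρ, into the apparent shape of that arm's decay curve.

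**Working it through.** **The plan's own figure.** The documents state no precision for infant GMTs or GMRs. The only sample-size calculation is Protocol Table 6, on detecting an adverse event. Its worked example reproduces: 1 − 0.99^100 = 0.634, against the stated 63%. It has no bearing on the width of infant titer intervals.

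**Inputs**
- Arm size N: 100 in the northern hemisphere (Protocol 9.2, note to Table 6), and up to 650/5 = 130 with both hemispheres (Protocol 4.1.2). Both are before losses.
- Infants bled at a later visit, m: N/2, so 50 or 65. The 1:1 split is an assumption.
- ρ, the within-arm correlation of log birth titer and log titer at the visit: not given; shown over a range.
- SD of log titer: not given. It cancels from the ratios; 1.0 on the natural-log scale is assumed for one illustration.

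**Formulas**
- Planned variance of an arm's log mean: SD²/m.
- Regression estimator: fit log later titer on log birth titer among the m bled infants, then predict at the mean log birth titer of all N. Variance ≈ (SD²/m) × [1 − ρ²(1 − m/N)].
- With m/N = 1/2, the ratio to the planned variance is 1 − ρ²/2. Each arm is projected to its own birth mean, so the same factor applies to the log GMR when ρ is equal in both arms.
- Interval width ratio: √(1 − ρ²/2). Effective number bled: m/(1 − ρ²/2).

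| ρ (assumed) | Variance ratio | Width ratio | CI narrower by | Effective n from 50 | Effective n from 65 |
|---|---|---|---|---|---|
| 0.3 | 0.955 | 0.977 | 2% | 52 | 68 |
| 0.5 | 0.875 | 0.935 | 6% | 57 | 74 |
| 0.7 | 0.755 | 0.869 | 13% | 66 | 86 |
| 0.9 | 0.595 | 0.771 | 23% | 84 | 109 |
| 1 (limit) | 0.500 | 0.707 | 29% | 100 | 130 |

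**Cost of estimating the slope.** This adds about (1 − ρ²)(1 − m/N)/(m − 3) to the variance ratio. At ρ = 0 and m = 50 that is 0.5/47 = 0.011, about 1%. Simulation of the within-arm estimator agreed: ratios of about 0.96, 0.88, 0.76 to 0.77 and 0.59 at ρ = 0.3, 0.5, 0.7 and 0.9, with no bias and about 95% coverage.

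**On the GMR scale.** Take N = 100 and an assumed SD of 1.0. The planned half-width is 1.984 × √(2/50) = 0.397, so the 95% CI is the GMR multiplied and divided by 1.49. It becomes 1.45 at ρ = 0.5, 1.41 at 0.7 and 1.36 at 0.9. Bleeding all 100 infants at that visit would give 1.32.

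**Chance imbalance between halves.** The SE of the difference in mean log birth titer is SD × √(1/50 + 1/50) = 0.2 SD, and this carries into the later means in proportion to ρ.

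**If the split is not 1:1.** At ρ = 0.7, the ratio is 1 − 0.49 × 0.4 = 0.80 for a schedule holding 60% of infants and 1 − 0.49 × 0.6 = 0.71 for one holding 40%.

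**The case against.** The strongest reply is that nothing in the plan is wrong. Schedules are random, every analysis is declared descriptive, there is no decision rule, and no precision target exists to be missed. That stands. A reader might infer that the visit means, or the decay curve drawn through them, are biased. The documents do not support that. Assignment precedes any infant titer, and chance imbalance between the halves is ordinary sampling error that the planned t intervals already cover.

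The size of the gain is also open. Exponential decay implies no particular correlation, and the documents give reasons why ρ could be low at 6 months:
- Vaccination is timed so that infants are likely to meet RSV in their first 6 months (Protocol 4.1), and infection may raise some titers.
- The 6-month window runs from 168 to 210 days (Protocol 1.3.2).
- Values below the LLOQ are set to half of it (SAP 5.3.2).

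All of this stands, and it is why the gain is given as a range starting near zero.

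A reader might also infer that dose selection hangs on these GMRs. SAP 2 places the selection criteria outside the SAP. The first planned analysis is triggered by cord-blood titers (SAP 7.2), and the formulation-by-dose model uses maternal 1-month titers (SAP 6.2.1.1.2). No readable text ties selection to the later infant GMRs.

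Two smaller points stand. The evaluable rule asks for at least one valid birth result and does not say that both RSV A and RSV B are needed, so birth data may be slightly incomplete for one subgroup. Birth samples may also mix cord and venous blood.

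The descriptive label does not dispose of the point, because intervals are what a descriptive study reports and these can be narrowed using samples already taken.

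**Conclusion.** The point holds as a loss of precision in the readable secondary infant analysis. The 1-, 2-, 4- and 6-month GMTs and GMRs are valid as planned, but they make no use of the birth titers of infants assigned to the other schedule. Depending on ρ, log-scale intervals could be about 2% to 23% narrower over the range 0.3 to 0.9, with a ceiling of 29%. If ρ is zero, the cost is about 1% in variance.

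This rests on an assumed 1:1 schedule split and an assumed ρ that may differ by visit and arm. It does not show that the trial lacks any persistence model, because the redacted sections may contain one. It is a low-cost improvement to a sound analysis, and no error needs correcting.

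**What to change.** In SAP 6.2.2.1.1, keep the raw GMTs and GMRs as planned and add the following at 1, 2, 4 and 6 months, separately for each visit and for RSV A and RSV B:

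1. Within each arm, regress log titer at the visit on log birth titer among infants bled at that visit.
2. Predict the arm mean at the mean log birth titer of all evaluable infants in that arm with a birth result for that subgroup.
3. Form GMRs from these arm means, with regression-estimator or bootstrap confidence intervals.

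Do not condition the GMR on birth titer. It is measured after maternal vaccination, so equalising it between arms would remove part of the vaccine effect.

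Do not substitute a mixed model with an infant random intercept. That model forces equal correlation between all visits. In simulations where correlation fell with time, its 6-month standard errors were roughly 4 to 9% too small and its nominal 95% intervals covered about 92 to 94%. An unstructured covariance is also unsuitable, because visits from different schedules are never observed in the same infant.

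The cost is SAP wording and a short program, with no extra bleed, visit or participant. The downsides are a working linear relation between log titers and a second set of estimates to report. Stating the schedule ratio in the SAP would also help.
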